#### 7.B.3.6. Medico-economic evaluation

The medico-economic evaluation in terms of costs will be performed in each country separately by the medico-economics consultants. It will be carried out on the ITT data set (*defined in section 7.B.3.1*), using the observed case approach, without any extrapolation of missing data on all data recorded throughout the *Follow-Up Period*.

### MAIN EVALUATION OF OVERALL COSTS

Average overall individual costs per month will be tabulated in each country, as quantitative data, by study group, from the perspective of the health care payer (*as defined in section 6.C.1*).

The main medico-economic evaluation performed will be the comparison of these average overall monthly costs between both study groups, in each country where the number of randomised patients allows the performance of this analysis, separately, using the Student's t test or the Wilcoxon's rank sum test, depending on the shape and type of the distribution of the national overall individual costs per month recorded.

If the number of randomised patients in a given country does not allow the performance of this country-based analysis, the overall resources used for the patient's medical management collected in volume in all participating countries pooled together will be priced globally with the national tariffs system in force in the given country, before being compared between both study groups, using either the Student's t test or the Wilcoxon's rank sum test.

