### **6.C.3 Cost-utility**

An incremental cost per Quality-Adjusted Life Year (QALY) gained will be estimated by calculating the ratio between the incremental cost of the Intervention group (*receiving the Home-Based Disease Management Program*) and the Control group (*receiving the usual COPD education and follow-up of their investigational centre*) and the incremental utility.

The incremental cost will be estimated by calculating the difference between the average total costs per patient (*from the date of Visit 1 (included) onwards*) in both study groups.

Incremental utility will be estimated by using the self-evaluations of the 15D health-related quality of life instrument and the Finnish scoring algorithm. QALY weights will be calculated for each six-month study period, and they will be applied to the time period lived throughout the 12-month *Follow-Up Period*.

QALYs per patient in both study groups will be compared and, if relevant, related to the additional incremental cost required to produce one additional QALY (*incremental cost-utility analysis, as detailed in section 7.B.3.6*).

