### **7.B.2**     *Determination of sample size*

The primary objective of this phase IV study is to show that the set-up of the Home-Based Disease Management Program in patients with GOLD III/IV COPD reduces the individual yearly duration of unscheduled hospitalisations whatever their reason. Based on published results and assuming:

- an expected difference of 10 days of hospitalisation between the average individual yearly duration of unscheduled hospitalisation whatever their reason observed in the Intervention group and in the Control group,
- an estimated common standard deviation of 25 days,
- a type I error set to  $\alpha = 0.05$  (*two-sided conditions*),
- and  $(1-\beta)$  power equal to 0.90,

and using the nQuery Advisor® software Version 6.01 and the estimation provided for the Wilcoxon (*Mann-Whitney*) rank-sum test for a continuous outcome, the number of patients required is estimated to be 143 per study group.

With an expected 25.0% dropout rate per year over the *Follow-Up Period* (*i.e., at most 6.25% over the first 3 months (between Visit 1 and Visit 2) with no available individual data allowing the estimation of the primary efficacy criterion (as detailed in section 7.B.3.5) for the concerned patients*), this sample size estimation results in randomising around 306 patients, *i.e.,* approximately 153 patients in the Intervention group and 153 patients in the Control group.

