## **COST-EFFECTIVENESS**

If this main medico-economic evaluation reveals a statistically significant study group difference, at level  $\alpha = 0.05$ , in a given country, in a second step, the overall costs per patient, from the perspective of the health care payer will be related to the primary efficacy criterion, by estimating a cost per unscheduled hospital day avoided whatever its reason in each study group, separately.

Average overall costs and benefits will be estimated with Kaplan-Meier's sample averages and bootstrap replications, before calculating the 95.0% confidence intervals of Incremental Cost-Effectiveness Ratios (*ICERs, i.e., the overall net costs (defined as the difference in overall costs on the Home-Based Disease Management Program – those on the usual program) divided by the corresponding net benefits (i.e., the difference in both numbers of unscheduled hospital days whatever their reason)*).

If performed, this cost-effectiveness evaluation will be repeated, by relating the overall costs per patient, from the perspective of the health care payer, to the number of deaths, in each study group separately, by replacing the previous denominator of the calculated ICERs by the difference in the numbers of deaths in both study groups.

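### The main cost test gives a patient followed for a few weeks the same weight as a full-year patient, and its p-value decides whether cost-effectiveness and cost-utility are analysed at all

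*Protocol*

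**What the plan says.** Protocol section 7.B.3.6, under the main evaluation of overall costs: "Average overall individual costs per month will be tabulated in each country". It continues: "The main medico-economic evaluation performed will be the comparison of these average overall monthly costs between both study groups", country by country where numbers allow, with Student's t or Wilcoxon chosen from the shape of the recorded distribution. Where a country is too small, resources pooled over all countries are priced at that country's tariffs and tested in the same way.

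The data are those of the ITT set, as observed and without extrapolation. Section 7.B.3.1 puts everyone who entered the Follow-Up Period in that set, with no minimum follow-up. Section 7.B.2 expects 25% dropout per year, and sections 3.D and 4.B.5 count death as a reason for withdrawal. No weight for follow-up and no censoring adjustment is stated for this test.

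The cost-effectiveness part of 7.B.3.6 opens with a condition: "If this main medico-economic evaluation reveals a statistically significant study group difference", at the 0.05 level in the given country. The cost-utility part carries the same condition. Once past it, costs and benefits are estimated by Kaplan-Meier sample averages with bootstrap. Section 6.C.3 obtains the incremental cost by "calculating the difference between the average total costs per patient". Sections 6.C.2 and 6.C.3 attach no significance condition on cost to either analysis; 6.C.3 only makes relating QALYs to cost subject to relevance.

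**The concern.** A monthly cost computed over a short follow-up is a noisy number, and an admission just before an early death makes it very large. Giving it the same weight as a number based on a full year lets a handful of patients inflate the variance. Wilcoxon limits that, but it answers a different question: the numerator of the incremental ratio is a difference in mean cost, and a rank test can point elsewhere when costs are skewed.

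The test also acts as a gate. Section 2.B makes it a secondary objective to relate the cost difference to a difference in clinical outcome. Under 7.B.3.6 that objective is pursued only if the cost test is significant. A programme that saves hospital days at about the same cost would be stopped at this gate, although that is a result a payer would want to see.

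**Working it through.** **The plan's own figure.** Section 7.B.2 assumes "an expected difference of 10 days of hospitalisation between the average individual yearly duration", "an estimated common standard deviation of 25 days", two-sided alpha 0.05 and "power equal to 0.90". With p = Φ(10/(25√2)) = 0.611, Noether's formula gives n per group = (1.960 + 1.282)² / [6 × (0.611 − 0.5)²] ≈ 141.2, so 142 against the stated 143. Dropout: 143/(1 − 0.0625) = 152.5, so 153 per group and 306 in total. Both agree with the plan within rounding or software differences. No power is stated for the cost test.

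**How many short follow-ups.** At 25% per year with constant hazard, the share gone by day t is 1 − 0.75^(t/365): 2.2% by 28 days and 3.3% by 42 days. That is about 3 and 5 of 153 per arm.

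**Why they matter.** One 10-day stay is 10/12 = 0.83 days per month over a year but 10/1 = 10 over one month, a factor of 12. If admissions arrive at a constant rate, the within-patient variance of cost/T is proportional to 1/T, so it is also 12 times larger at one month.

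**Simulation.** There were 800 trials per scenario, with a Monte Carlo error of at most √(0.25/800) = 1.8 points. Dropout is the protocol's 25% per year. The other inputs are assumptions: 1.3 admissions per year with gamma frailty; lognormal stays with median 8 days; 450 per hospital day; 150 per month otherwise; true admission rate ratio 0.6. Three exit mechanisms were tried at 153 per arm:

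| Exits | t on cost/month | Wilcoxon on cost/month | Total cost / total months | Share of t-test sum of squares from those followed ≤ 6 weeks |
|---|---|---|---|---|
| Unrelated to admissions | 68% | 66% | 71% | 7% |
| Frailer patients leave earlier | 62% | 70% | 69% | 12% |
| Half of exits are deaths after a terminal stay | 28% | 56% | 64% | 49% |

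In ranks, the patients followed 6 weeks or less carry 3-4% in the first two rows and about 6% in the third.

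**Check of the third row.** The mean monthly difference is −216 with SD 165 for the unweighted comparison, and −199 with SD 88 for the ratio of totals. Then 216/165 = 1.31 and Φ(1.31 − 1.96) ≈ 26%; 199/88 = 2.26 and Φ(2.26 − 1.96) ≈ 62%. Both are close to the simulated 28% and 64%. A further simulation under assumed costs gave 30%, 59% and 70% (SD 156 against 84) for terminal stays, and 67%, 68% and 74% for unrelated exits.

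**Null.** With rate ratio 1, rejection was 3.6% to 6.6% across all tests and scenarios.

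**Per country.** An equal split over four countries (assumed) gives 153/4 ≈ 38 per arm. With terminal stays, power is then 14% (t), 20% (Wilcoxon) and 24% (ratio of totals). With unrelated exits it is 24%, 24% and 25%. The further simulation put it at about 11-23%.

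**The case against.** The strongest reply is that skewed hospital costs would probably send the analysis to Wilcoxon, where short-follow-up patients have little leverage and the worst-case loss is modest (56-59% against 64-70%). This stands as far as leverage goes. It does not answer the second difficulty, that a rank test does not examine the mean cost difference used in the ratio.

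Second, the size depends on inputs that the protocol does not give. This stands. A halved admission rate, half of exits as deaths with a terminal admission, and a 7-day minimum follow-up gave 20% against 84%; raising the minimum to 30 days alone moved the 20% to 35%. No single contrast should be quoted as the loss.

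Third, the divisor for monthly cost is undefined, and section 7.B.3.3 leaves missing-data handling to the analysis plan. This partly stands. Cost over months followed is a reading, though the primary criterion is normalised by days followed in the same way (7.B.3.5). The tested variable and the gate are fixed in the protocol itself.

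Fourth, section 7.B declares all medico-economic results exploratory and descriptive. That limits the stakes and leaves the primary conclusion untouched. It also makes a significance gate harder to justify.

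Fifth, the cost quantities in 6.C.3 and in the ratio of 7.B.3.6 agree with each other. This is correct: the odd one out is the monthly cost in the gate.

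**Conclusion.** The point holds as a weakness of the tested variable and of its use as a gate. Short follow-up gets full-year weight. On the t branch, with exits that end in hospital, this cuts power to about 30% against 64-70% at 153 per arm. With exits unrelated to admissions the loss is small, about 67% against 71-74%. These figures rest on assumed costs, an admission rate ratio of 0.6 and pooled numbers, and the comparator simulated was total cost over total months; the Kaplan-Meier sample average was not simulated.

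A reader might infer three stronger things that the documents do not support:

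- That patients with a few weeks of follow-up dominate the test in general. They do so only on the t branch and only when exits follow admissions; the protocol fixes neither.
- That the test is biased or yields false positives. The mean of monthly costs is a different quantity from total cost over total months, and rejection under the null stayed near 5%.
- That a better estimator alone would let the economic analyses run. At about 38 per arm per country, power is roughly 11-25% by any method, so the gate itself is the main obstacle.

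**What to change.** - Make the main cost comparison in 7.B.3.6 the difference in mean 12-month cost per patient, by the Kaplan-Meier sample averages and bootstrap already planned for the ratios. Total cost over total patient-months with bootstrap is an acceptable alternative. State which is used, because the two differ when patients die.
- Drop the t/Wilcoxon test on individual monthly costs as the condition for going further. If monthly costs are still tabulated, define the divisor.
- Report the cost-effectiveness and cost-utility ratios with their uncertainty whatever the cost p-value.
- Reconcile 6.C.2 and 6.C.3 with 7.B.3.6 on whether these analyses are conditional, keeping the mean total cost per patient of 6.C.3 as the common quantity.

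The cost is analysis wording and slightly more reporting. No new data are needed, and the estimator is already to be programmed. Per-country estimates will remain imprecise, and wide intervals should be shown as such.

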## **COST-EFFECTIVENESS**

If this main medico-economic evaluation reveals a statistically significant study group difference, at level  $\alpha = 0.05$ , in a given country, in a second step, the overall costs per patient, from the perspective of the health care payer will be related to the primary efficacy criterion, by estimating a cost per unscheduled hospital day avoided whatever its reason in each study group, separately.

Average overall costs and benefits will be estimated with Kaplan-Meier's sample averages and bootstrap replications, before calculating the 95.0% confidence intervals of Incremental Cost-Effectiveness Ratios (*ICERs, i.e., the overall net costs (defined as the difference in overall costs on the Home-Based Disease Management Program – those on the usual program) divided by the corresponding net benefits (i.e., the difference in both numbers of unscheduled hospital days whatever their reason)*).

If performed, this cost-effectiveness evaluation will be repeated, by relating the overall costs per patient, from the perspective of the health care payer, to the number of deaths, in each study group separately, by replacing the previous denominator of the calculated ICERs by the difference in the numbers of deaths in both study groups.

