Additionally, **secondary criteria** will be evaluated including frequency of moderate and severe COPD exacerbations, use of health care services due to COPD and to all causes, compliance to oxygen therapy, if applicable, health-related quality of life, clinical outcome measurements and safety parameters. The education program is expected to reduce the frequency of severe COPD exacerbations and to increase patient health-related quality of life towards supporting independence and self-management and encouraging positive health behaviours. Particular attention will be paid to compliance to long term oxygen therapy (LTOT). Indeed, the benefit of LTOT on survival is strongly associated with the average daily treatment duration, and poor LTOT compliance is a predictor of hospital admissions in hypoxemic COPD patients. Inconvenience, fear and overall misunderstanding of the role of supplemental oxygen result in daily usage which is generally less than prescribed, but that can be improved by proper patient education. For study patients on oxygen therapy, compliance will be assessed using the medical device *NOWOX* which records daily hours of oxygen use and breathing frequency. Survival, rate of lung function decline, and functional ability will also be evaluated, but no significant benefit is expected from the program with regards to these parameters, as previously demonstrated.

In addition to benefits for individual patients, this COPD management program may also meet societal goals in decreasing the cost of COPD care by reducing hospital admissions and the hospital length of stay. Therefore, a **medico-economic evaluation** will also be performed based on intervention-specific cost of care, global cost of patient care, and patient utility. As the cost of medical services is highly dependent on local factors, and may vary substantially between countries, national medico-economic evaluations will be performed in each participating country.

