## **COST-UTILITY**

In the same manner, if the main medico-economic evaluation reveals a statistically significant study group difference, in a given country, a cost-utility evaluation will be performed, in the same way as the cost-effectiveness evaluation, the denominator of the calculated ICERs being in that case, the difference in QALYs (*as defined in section 6.C.3*).

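### The planned confidence interval for the cost-effectiveness ratio is the same for a dominant and a dominated programme, its denominator has no stated direction, and for deaths it will usually be uninterpretable

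*Protocol*

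**What the plan says.** Section 7.B.3.6 (Cost-effectiveness) applies in a country only if the comparison of monthly costs there is significant at 0.05. Average costs and benefits are then bootstrapped "before calculating the 95.0% confidence intervals of Incremental Cost-Effectiveness Ratios".

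- The numerator has a direction: "the difference in overall costs on the Home-Based Disease Management Program" minus those on the usual programme.
- This is "divided by the corresponding net benefits", which are defined as "the difference in both numbers of unscheduled hospital days whatever their reason".
- The evaluation is repeated for deaths "by replacing the previous denominator of the calculated ICERs by the difference in the numbers of deaths in both study groups".
- Under Cost-utility, the same method is used, "the denominator of the calculated ICERs being in that case, the difference in QALYs".

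Section 1.C says of survival, among other parameters, that "no significant benefit is expected from the program with regards to these parameters". Section 2.B includes relating the cost difference to a difference in clinical outcome among the secondary objectives. Section 7.B makes all medico-economic results exploratory and descriptive.

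**The concern.** A ratio of two differences does not keep their signs. If the interval for the ratio is the inferential result, it cannot by itself separate the best outcome for the programme (cheaper and better) from the worst (dearer and worse).

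Two features of the text add to this. First, the denominator is called a benefit but is defined as a difference in something undesirable, and the order of subtraction is not given. Two analysts could report opposite signs from the same data. The same section also asks for a cost per day avoided within each study group, although days avoided exist only as a contrast between groups. Second, the deaths ratio divides by a quantity that the protocol itself expects to be near zero, where a ratio has no stable interval.

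At stake is whether the interval for a secondary objective can be read at all.

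**Working it through.** **The plan's own figures.** The protocol gives no ICER value to reproduce. The check borrows three inputs from section 7.B.2: a difference of 10 days, an SD of 25 days and 143 evaluable patients per group. That sample size is sound. P = Φ(10/(25√2)) = 0.611, and Noether's formula gives (1.960 + 1.282)² / (12 × 0.25 × 0.1114²) ≈ 282.5 in total, or 142 per arm against 143 stated. Then 143/0.9375 = 152.5, so 153 per arm and 306 in all.

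**Step 1: sign of the ratio.** Assume a cost difference of ±3000 currency units and ±10 days.

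| Result for the programme | Days as Intervention − Control | Days avoided (Control − Intervention) |
|---|---|---|
| Saves, fewer days (dominant) | −3000/−10 = +300 | −3000/10 = −300 |
| Costs more, more days (dominated) | 3000/10 = +300 | 3000/−10 = −300 |
| Costs more, fewer days | −300 | +300 |
| Saves, more days | −300 | +300 |

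The ambiguous sign is positive under Intervention minus Control and negative under days avoided. Deaths behave like days. For QALYs gained the ambiguous sign is negative.

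**Step 2: the interval.** If every replicate pair (C, D) is replaced by (−C, −D), each ratio C/D is unchanged. Any interval built from the ratios alone is then unchanged too. A normal approximation to the bootstrap confirms this, using the protocol's 10 days and SD 25, with an assumed cost difference of 4000, cost SD 8000 and correlation 0.9. The 95% percentile intervals are:

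- 143 per arm: 317 to 596 (dominant) and 317 to 595 (dominated).
- 36 per arm (143/4, one country of four): −208 to 1255 and −196 to 1247.

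The small gaps are simulation error.

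**Step 3: denominator near zero, days.** At 143 per arm the standard error of the day difference is 25√(2/143) = 2.96. A true 10-day difference lies 3.4 standard errors from zero, so the days ratio is stable there and its only problem is Step 1. With no true day difference and an assumed cost difference of 3000 (SD 6000, z = 3000/(6000√(2/143)) = 4.2), half the replicates fall on each side of zero. The interval then runs from about −16,000 to +16,000, although costs clearly differ.

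**Step 4: denominator near zero, deaths.** Call the denominator straddling if more than 2.5% of its replicates lie on each side of zero. To a normal approximation this happens when |observed difference|/SE < 1.96.

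- 15% in both arms: probability 0.95 at any size.
- 15% versus 10%, 143 per arm: SE = √[(0.1275 + 0.09)/143] = 0.0390 and 0.05/0.0390 = 1.28, so Φ(0.68) − Φ(−3.24) ≈ 0.75.
- 15% versus 10%, 38 per arm (153/4): SE = 0.0757 and the ratio is 0.66, so Φ(1.30) − Φ(−2.62) ≈ 0.90.

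Simulation with actual bootstrap replicates, counting only trials that pass the cost-significance condition and using assumed costs, gives roughly 84–95% at equal mortality and roughly 69–83% at 15% versus 10%. These run somewhat below the approximation. One reason is that death counts are small and replicates exactly at zero fall on neither side. The condition acts on cost, so it does little to move the deaths difference away from zero.

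**The case against.** The strongest reply is that the ratio is never read alone. It is computed only after a significant cost difference, so the sign of the numerator is normally known. With no true effect on days, only about 5–10% of simulated trials get that far. With the expected 10-day benefit, 24–75% do at 38 to 76 per arm, and 99.7–100% of those land in the quadrant where the programme saves money and avoids days. Costs are tabulated by group (7.B.3.6), hospital days are compared as the primary analysis (7.B.3.5), deaths are described by group (7.B.3.3) and QALYs are compared (6.C.3). All of this stands. A reader might infer that the economic evaluation cannot tell success from failure, or that the secondary objective goes unanswered; the documents do not support that.

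A reader might also infer that a positive ICER is always the ambiguous one. That holds only for Intervention minus Control days or deaths. The protocol's own wording about benefits and days avoided points the other way, and section 6.C.3 speaks of QALYs gained, where the ambiguous sign is negative.

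It is also fair that the protocol names no bootstrap interval method and that plots and acceptability curves can be left to an analysis plan. But Step 2 holds for any interval built from the ratios alone, and the choice of a ratio interval is stated in the protocol, not left open. The cost-significance condition and the companion tables help the reader; they do not repair the interval.

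**Conclusion.** The point holds as a defect of the planned interval. The algebra needs no assumptions: mirrored dominant and dominated results give the same ratio and interval, under either direction of the denominator. The missing direction for days and deaths is plain from the text.

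For days, at the planned effect and full sample size, the problem is sign ambiguity and not instability. For deaths the interval will usually be uninterpretable: roughly 84–95% of trials reaching this step at 15% mortality in both arms, and roughly 69–83% at 15% versus 10%. Those shares rest on assumed mortality, costs and country sizes, because the protocol gives none of them.

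Severity is minor. The analysis is exploratory, and the components reported elsewhere usually identify the quadrant.

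**What to change.** In section 7.B.3.6:

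1. Define the denominators as days avoided and deaths avoided (Control minus Intervention) and QALYs gained (Intervention minus Control).
2. From the same bootstrap replicates, report the cost difference and the outcome difference, each with a 95% confidence interval, and the share of replicates in each quadrant of the cost-effectiveness plane.
3. Do not report a confidence interval for the ICER when the denominator's replicates straddle zero or when the result is dominant or dominated.
4. Express joint uncertainty as incremental net benefit over a stated range of willingness-to-pay values.

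The cost is a change of wording and a little more analysis. No new data, patients or visits are needed, and the replicates are already planned. The one new decision is the willingness-to-pay range for each outcome.

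### Section 7.B.3.6 asks for a cost per hospital day avoided within each study group, which is undefined, and leaves the scale of the deaths ratio unfixed

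*Protocol*

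**What the plan says.** Section 6.C.2 defines cost-effectiveness as a cost difference between the two programmes set against a difference in medical outcome over the 12-month Follow-Up Period. It names two outcomes: unscheduled hospital days and the number of deaths.

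Section 7.B.3.6 (Cost-effectiveness) applies only in a country where the main cost comparison is significant at 0.05. It has three steps.

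- **Hospital days, first paragraph.** Overall costs per patient are related to the primary criterion "by estimating a cost per unscheduled hospital day avoided whatever its reason in each study group, separately".
- **Hospital days, second paragraph.** "Average overall costs and benefits will be estimated with Kaplan-Meier's sample averages and bootstrap replications". The incremental cost-effectiveness ratio (ICER) then has net costs as its numerator, "defined as the difference in overall costs on the Home-Based Disease Management Program – those on the usual program", and as its denominator "the difference in both numbers of unscheduled hospital days whatever their reason".
- **Deaths, third paragraph.** The evaluation is run a second time "by relating the overall costs per patient, from the perspective of the health care payer, to the number of deaths, in each study group separately", and this is done "by replacing the previous denominator of the calculated ICERs by the difference in the numbers of deaths in both study groups".

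For the separate cost-utility analysis, section 6.C.3 fixes the numerator per patient: "The incremental cost will be estimated by calculating the difference between the average total costs per patient".

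**The concern.** Two things in this short section do not fit together.

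First, a day avoided is a contrast with what would have happened under the other programme. An estimate made in each group separately has no such contrast, so the instruction cannot be carried out as worded.

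Second, when deaths replace hospital days, the cost side is still described per patient while the outcome becomes a difference in numbers of deaths. Hospital days have a natural per-patient scale: section 6.A.1 counts them for each randomised patient, and section 7.B.3.5 annualises them individually. Deaths have no such scale until they are divided by the number of patients or expressed as a risk, and the section does not say that this is done.

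Two analysts could each follow the text and report costs per death averted that differ by a factor equal to the arm size. A figure that is too small makes an added cost look like good value, or a saving look trivial. Relating the cost difference to clinical outcome is part of a secondary objective (section 2.B), so the ratio should be unambiguous.

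**Working it through.** **1. The within-group ratio**

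Write C for mean cost and D for mean hospital days per patient, with subscripts I (Intervention) and C (Control). A cost per day avoided is

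(C_I − C_C) / (D_C − D_I).

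Both parts need both groups. This is the form that section 6.C.2 describes and that the second paragraph of 7.B.3.6 defines. With one group alone, neither difference can be formed. The only ratio left is cost over days, which answers another question. With assumed figures:

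- Control: 9,000 / 15 days = 600 per day.
- Intervention: 5,000 / 5 days = 1,000 per day.

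The programme is cheaper and has fewer days, yet its ratio is higher. The protocol neither defines this ratio nor says that it would rank the groups. The example shows only that it is no substitute for the missing quantity.

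**2. The deaths ratio**

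Inputs from the protocol:

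- 153 patients per arm (7.B.2)
- four countries (4.A)
- evaluation by country, with pooled resource use priced at one country's tariffs where that country is too small (7.B.3.6)

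Section 7.B.3.6 states no numerical ratio to reproduce. The arm size does reproduce. Noether's formula with p = Φ(10 / (25√2)) = 0.611 gives 141.2, so 142 per arm against the stated 143. Then 143 / (1 − 0.0625) = 152.5, so 153 per arm and 306 in total.

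Assumptions, for illustration only: extra cost of 1,000 per patient, death risks of 10% (Intervention) and 15% (Control), and four countries of equal size, so 153 / 4 ≈ 38 per arm.

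- Both parts per patient: 1,000 / (0.15 − 0.10) = 20,000 per death averted.
- Literal reading, cost per patient over the difference in death counts:

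| Patients per arm (I, C) | Difference in deaths | Literal ratio | Factor too small |
|---|---|---|---|
| 153, 153 | 0.05 × 153 = 7.65 | 1,000 / 7.65 = 130.7 | 153 |
| 38, 38 | 0.05 × 38 = 1.9 | 1,000 / 1.9 = 526.3 | 38 |
| 40, 36 | 5.4 − 4.0 = 1.4 | 1,000 / 1.4 = 714.3 | 28 |

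With equal arms of n, the difference in deaths is n times the difference in risk. The factor is therefore exactly n, whatever cost and risks are assumed. With unequal arms it is not the arm size, as the last row shows.

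- Total cost over total deaths, equal arms: (153 × 1,000) / 7.65 = 20,000, a factor of 1.
- Mean cost over mean deaths per patient is the first calculation above, also a factor of 1.

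The mismatch therefore arises under one reading of the text and disappears under two others.

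**The case against.** The strongest reply is that the section supplies its own scale. It says that average costs and average benefits are estimated before any ICER is formed, and the deaths analysis repeats that evaluation with only the outcome exchanged. An average of deaths is a proportion, which is close to what one would want. The ICER definition also speaks of net overall costs without saying per patient, and the explicit per-patient difference in section 6.C.3 belongs to the cost-utility analysis. The word for numbers is used for hospital days as well as for deaths, so it need not mean a raw group total.

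This stands as far as it goes. A reader might infer that the deaths ratio is certainly wrong, by a factor of 153. The documents do not support that: a consistent reading is open, and 153 applies only if all countries are pooled, whereas the evaluation is planned by country. What the reply does not remove is the ambiguity. The benefits in the averaging paragraph are hospital days, and the next paragraph replaces that denominator while again naming costs per patient.

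A second reply is that the within-group phrase is a slip, since 6.C.2 and the following paragraph give a computable definition. It is true that the hospital-day ICER can be computed, and no one should conclude otherwise. The phrase is still an instruction that cannot be followed. It recurs for deaths, where the same sentence then defines a between-group difference.

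A third reply concerns weight. Section 7.B makes all economic results exploratory and descriptive, the analysis depends on a significant cost difference, and section 1.C expects no significant survival benefit. All of this is correct and limits the importance of the point.

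**Conclusion.** The instruction to estimate a cost per hospital day avoided in each group separately is wrong as stated. It is undefined without a comparator and conflicts with section 6.C.2 and with the ICER in the next paragraph. This part rests on no assumption.

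For deaths, the fault is a scale that is not fixed. If the wording is taken literally and the arms are equal, the ratio is too small by the arm size: about 38 with four equally large countries analysed separately (the equal split is an assumption), or 153 if everything is pooled. If the averaging sentence is carried over to deaths, there is no error. It would go too far to call this a proven arithmetical mistake, because no figure stated in the protocol is wrong.

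The consequences are confined to exploratory economic results. The primary analysis and the sample size are unaffected.

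**What to change.** In section 7.B.3.6:

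- Define the hospital-day ICER as the difference in mean cost per patient over 12 months divided by the difference in mean annualised unscheduled hospital days per patient.
- Define the deaths ICER with the same numerator, divided by the difference in the Kaplan-Meier probability of death at Month 12. Time to death by group is already planned in section 7.B.3.3.
- State the 12-month horizon for both parts of each ratio, since the main cost comparison is expressed per month.
- Delete the phrase that requires these ratios in each group separately, in both places. Report mean cost and mean outcome by group beside the incremental result.

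The cost is a few lines of wording. No new data, visits or patients are needed.
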